6.1.8 Health care resource use

For health care resource use parameters, the following will be evaluated: concomitant medications (see Section 6.1.5), medical procedures, health care provider consultations not foreseen by the protocol, and hospitalization/ER visits.

6.1.8.1 Medical procedures

The number of concomitant medical procedures per participant will be summarized for the Treatment Period. The number of concomitant medical procedures per participant will be summarized using the categories 0, 1, 2, and 3 or more.

Participants who had any concomitant medical procedures during the course of the study based on the Concomitant Medical Procedures eCRF module will be listed.

6.1.8.2 Healthcare provider consultations

The number of healthcare provider consultations per participant for the Treatment Period will be summarized. The number of healthcare provider consultations will be summarized using the categories 0, 1, 2, 3, 4, and 5 or more.

All healthcare provider consultations data will be listed.

6.1.8.3 Hospital stays and ER visits

The number of hospital stays per participant during the Treatment Period will be summarized. The number of hospital stays will be summarized using the categories 0, 1, 2, 3, 4, and 5 or more. The number and percentage of participants with specific reasons for duration of hospital stays will be summarized for the duration of the Treatment Period.

The durations of hospital stays for the Treatment Period will be summarized. Duration of hospital stays (as defined in Section 5.1.2.10) will be categorized as 0 days, 1-5 days, 6-10 days, 11-15 days, and >15 days, and summarized for the duration of the Treatment Period.

An event logged on the Hospitalization/ER Visit eCRF module where ER is marked as initial entry point will be defined as an ER visit. An ER visit with a participant transfer to an inpatient general ward will also be counted as a hospitalization. However, all other instances of ER visits (where participant transfer is not to an inpatient general ward) will not be counted as hospitalizations. Descriptive statistics for the number of ER stays during the Treatment Period will be presented. The number of ER visits will be summarized using the categories 0, 1, 2, and 3 or more. The number and percentage of participants with specific reasons for duration of ER visits will be summarized for the duration of the Treatment Period.

Hospitalizations with either a partial admission or discharge date are ignored for the calculation of duration of hospital stay. However, such hospitalizations are counted for the number of hospital stays. Participants with no hospital stays will have a duration of 0 days. Should distinct records for hospital stays overlap, then the days during the overlap will only be counted once. Similarly this also applies for ER visits.

All hospitalization and ER data will be listed.

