## Definition of SAE

If an event is not an AE per definition above, then it cannot be an SAE even if serious conditions are met (eg, hospitalization for signs/symptoms of the disease under study, death due to progression of disease).

An SAE is defined as any untoward medical occurrence that, at any dose:
--

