**c. Requires inpatient hospitalization or prolongation of existing hospitalization**

In general, hospitalization signifies that the participant has been detained (usually involving at least an overnight stay) at the hospital or emergency room for observation and/or treatment that would not have been appropriate in the physician’s office or outpatient setting. Complications that occur during hospitalization are AEs. If a complication prolongs hospitalization or fulfills any other serious criterion, the event is serious. When in doubt as to whether “hospitalization” occurred or was necessary, the AE should be considered serious.

Hospitalization for elective treatment of a pre-existing condition that did not worsen from baseline is not considered an AE.

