5.1.2.10 Hospital stay duration

The duration of each hospital stay will be calculated as the discharge date minus the admission date (Hospitalization/Emergency Room [ER] Visit Date on the eCRF module) plus 1 day for hospital stays with a discharge date.

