6 SUPPORTING DOCUMENTATION

6.1 Appendix 1 Non-key analysis specifications

6.1.1 Baseline characteristics and demographics

Demographics and baseline characteristics will be summarized descriptively for the SS. The summary comprises age (years) at entry into EP0151, age (years) at entry into first pediatric study, and age at entry into EP0151 categorized as (24 months - <12 years), racial group (American Indian/Alaskan Native, Asian, Black, Native Hawaiian or Other Pacific Islander, White, and Other/Mixed), ethnicity (Hispanic or Latino, and not Hispanic or Latino), weight (kg), height (cm) and BMI (kg/m^2). The number of participants and percentage for age groups, gender and countries will also be presented for the SS.

Demographic data will also be listed for the SS.

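### As worded, SAP 6.1.8.3 gives no hospital stay to a child admitted from the ER only to an inpatient unit other than a general ward (minor; non-key tables)

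*SAP*

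**What the plan says.** SAP 6.1.8.3 decides what counts as a hospital stay in three steps.

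- Entry point: "An event logged on the Hospitalization/ER Visit eCRF module where ER is marked as initial entry point will be defined as an ER visit".
- Some ER visits count in both tables: "An ER visit with a participant transfer to an inpatient general ward will also be counted as a hospitalization".
- The remainder is closed off: "all other instances of ER visits (where participant transfer is not to an inpatient general ward) will not be counted as hospitalizations".

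The SAP does not define an inpatient general ward, and no sentence extends the term to intensive care or a specialist unit. Stays per participant are tabulated as 0, 1, 2, 3, 4, and 5 or more. Durations are tabulated as 0, 1-5, 6-10, 11-15 and more than 15 days. At the bottom of the scale, "Participants with no hospital stays will have a duration of 0 days". For a counted stay, SAP 5.1.2.10 gives the length: "The duration of each hospital stay will be calculated as the discharge date minus the admission date", plus 1 day.

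The same section also plans an ER-visit count, a summary of reasons relating to ER visits, and a listing of every hospital and ER record. All of it sits in SAP Appendix 1, titled "Non-key analysis specifications".

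**The concern.** The table is meant to count hospital stays, but for children who enter through the ER the test is the type of ward. A child who goes from the ER to intensive care and is discharged from there has been an inpatient, yet falls into the remainder that is not counted.

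Nothing in the section applies a ward test to a child admitted directly. The same unit and the same dates could therefore count for one route of entry and not for the other. The 0-day row could mix children who were never admitted with children admitted only to a unit other than a general ward.

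What is at stake is limited to the number and duration of hospital stays as tabulated.

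**Working it through.** The plan states no figure to reproduce, so the check applies the rule to each possible route.

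**Inputs.** The counting rule, the categories and the 0-day rule come from SAP 6.1.8.3. Length of stay (discharge minus admission plus 1) comes from SAP 5.1.2.10. The expected 80 to 100 participants come from Protocol 9.7 and SAP 3. The documents give no frequency of ER admission by unit, so none is assumed.

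**Rule by route.**

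| Route | ER visits | Hospital stays |
|---|---|---|
| ER, then general ward | 1 | 1 |
| ER, then home | 1 | 0 |
| ER, then only another inpatient unit | 1 | 0 |
| ER, then another unit, then general ward | 1 | 1 on a natural reading; the text does not say whether the transfer must be direct |
| Direct admission, no ER entry | 0 | not touched by the ward condition |

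The third row is the problem.

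**Size per affected child (illustration).** Take a child with no other event who enters the ER on day 1 and leaves intensive care on day 10.

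- If the event counted as a stay: 1 stay, (10 - 1) + 1 = 10 days, category 6-10 days.
- Under the rule as worded: 0 stays, 0 days.
- Shift in the percentage of children with no stay: 1/100 = 1.0 percentage point, or 1/80 = 1.25 percentage points.

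**Direction (illustration).** Take a child with two admissions of 2 and 10 days, one of which falls under the exclusion. Days are summed per child. The section suggests this, through its 0-day and overlap rules, but does not state it outright.

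- Both counted: 2 + 10 = 12 days, category 11-15; mean per stay 12/2 = 6.
- 2-day stay excluded: 10 days, category 6-10; mean per stay 10.
- 10-day stay excluded: 2 days, category 1-5; mean per stay 2.

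Stays and total days fall in both cases. A mean per stay, which the SAP does not name as a planned statistic, could move either way.

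**The case against.** The strongest objection is that the form is not shown. SAP 6.1.8.3 refers to the Hospitalization/ER Visit eCRF module by name, and inpatient general ward may be that module's response option for any inpatient transfer. If so, no child is miscounted and only a definition is missing. This stands as a condition on the finding. It does not remove the need for an edit, because the SAP as written does not say so.

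Three stronger readings are tempting and should not be adopted.

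- *That SAP 5.1.2.10 contradicts the rule.* It does not. It gives the length of a stay once there is one; SAP 6.1.8.3 decides whether there is one. The 10 days shown above are what the event would contribute if counted, not a competing result.
- *That the protocol's description of hospitalization contradicts the rule.* Protocol Appendix 3 says that "hospitalization signifies that the participant has been detained" and has no ward condition, but it is a seriousness criterion for SAEs and it includes detention in the emergency room. A resource-use table that separates ER visits from stays has to differ from it.
- *That disease-related admissions can never reach the SAE tables.* Appendix 3 does say of an event that "it cannot be an SAE even if serious conditions are met (eg, hospitalization for signs/symptoms of the disease under study", but only where the event is not an AE. The AE definition keeps signs and symptoms of the disease that are more severe than expected. Protocol Table 8-1 also lists convulsion and status epilepticus as anticipated SAEs, and these must still be reported. The gap is therefore limited to disease-related admissions judged not more severe than expected. For those, the SAE tables do not make up for the missing stay.

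It is also fair to object that the event is not lost. It remains in the ER-visit count, the summary of ER reasons and the listing.

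**Conclusion.** The point holds on the wording, as a minor one. SAP 6.1.8.3 is a closed rule. Followed exactly, it gives 0 stays to a child admitted from the ER only to a unit other than a general ward, and 0 days if that child has no other counted stay. Against a rule that counts any inpatient transfer, it can only lower stay counts and total days per participant.

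The size is 1.0 to 1.25 percentage points per affected child with no other stay, for 100 down to 80 participants. No total can be given, because the number of such children is unknown. Whether any child is actually miscounted depends on the transfer options on a form that is not shown.

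The effect is confined to non-key hospital-stay tables. SAE capture and the five primary endpoints do not use this rule and are unaffected.

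A separate disclosure point changes no result. Protocol 8.10 says that medical resource utilization is not evaluated, SAP 6.1.8 plans to evaluate it, and SAP 6.2 declares no changes to the protocol's planned analyses.

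**What to change.** If SAP 6.1.8 is kept:

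1. Reword the rule in SAP 6.1.8.3 so that an ER visit followed by transfer to any inpatient unit (general ward, intensive care or other), directly or indirectly, counts as a hospitalization. If the form's label already covers every inpatient unit, define it that way in the SAP instead.
2. List the resource-use summaries in SAP 6.2 as an addition to what Protocol 8.10 says is evaluated. This discloses the difference but does not remove it.

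The cost is one sentence and one entry. No new data are needed if the existing module records the unit of transfer, which is an assumption to check against the form. If SAP 6.1.8 is removed, neither edit is needed.

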6.2 Appendix 3: Changes to Protocol-Planned Analyses

No changes to protocol planned analyses.

